EQ-5D-5L		X								X															X		X
Mental Health Questionnaires																											
PHQ-9	X	X			X			X		X				X			X		X		X		X		X	X	X
	PHQ-9 is self-administered and should be completed after assessment of adverse events.																										
C-SSRS (Baseline/Screening Version)	X																										
	The C-SSRS should be administered after assessment of adverse events. For this study, the C-SSRS is adapted for the assessment of the ideation and behavior categories only. The Intensity of Ideation and Lethality of Behavior sections are removed.																										
C-SSRS (Since Last Visit Version)		X	X	X	X	X	X	X	X	X	X	X	X	X	X	X	X	X	X	X	X	X	X	X	X	X	
	The C-SSRS should be administered after assessment of adverse events and capture information since most recent C-SSRS administration. For this study, the C-SSRS is adapted for the assessment of the ideation and behavior categories only. The Intensity of Ideation and Lethality of Behavior sections are removed.																										
Self-Harm Supplement Form	X	X	X	X	X	X	X	X	X	X	X	X	X	X	X	X	X	X	X	X	X	X	X	X	X	X	
	The Self-Harm supplement form should be administered after assessment of adverse events.																										

Visit	1	2	3	4	5	6	7	8	9	10	11	12	13	14	15	16	17	18	19	20	21	22	23	24	99	ED	801	
Week of Treatment	-2	0	4	8	12	16	20	24	28	32	36	40	44	48	52	56	60	64	68	72	76	80	84	88	88		4 wks post end of TxP	
Allowable Interval Tolerance (days)		±3	±3	±3	±3	±3	±3	±3	±3	±3	±3	±3	±3	±3	±3	±3	±3	±3	±3	±3	±3	±3	±3	±3	±7	±7	±3	
Fasting Visit	X	X	X	X	X	X	X	X	X	X	X	X			X		X		X		X		X	X	X	X		
Telephone Visit													X	X		X	X		X	X		X	X					
Self-Harm Follow-up Form	X	X	X	X	X	X	X	X	X	X	X	X	X	X	X	X	X	X	X	X	X	X	X	X	X	X		
	Self-Harm Follow-up Form is only required if triggered by the Self-Harm Supplement Form, per instructions in the form.																											
Laboratory Tests and Sample Collections																												
Hematology	X				X			X			X														X		X	
HbA1c	X	X			X			X			X				X			X			X			X		X	X	
Chemistry panel (includes Cr for eGFR calculation and glucose)	X	X			X			X			X				X			X			X			X		X	X	
	The CKD-EPI equation will be used by the central lab to estimate and report eGFR.																											
Insulin		X			X			X			X				X			X			X			X		X	X	
C-peptide		X			X			X			X				X			X			X			X		X	X	
Lipid panel	X	X						X			X														X		X	X
Free fatty acids	X	X						X			X														X		X	X

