### ***Visit 99***

Visit 99 is only applicable to participants who discontinue the double-blind study treatment prematurely (after Week 36 and before Week 88) and decline to complete the remaining scheduled study visits. These participants will be asked to return for Visit 99 at 88 weeks  $\pm 7$  days (see Section 7.2.1.). This visit is critical to ensure complete data collection for the primary body weight endpoint.

Participants should attend this visit in the fasting state. Procedures to be completed are:

- measurement of weight and waist circumference
- listing of concomitant medications
- assessment of AEs, and
- completion of the Mental Health questionnaires (after the AE assessment).

For participants unwilling to attend this visit, their refusal to attend should be documented in the participant medical record.

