
To demonstrate that tirzepatide MTD is superior to placebo in change from randomization (Week 36) for the following (measured at 88 weeks):
 
 BMI Glycemic control Insulin Lipid parameters Blood pressure Patient-Reported Outcomes 
To demonstrate that tirzepatide MTD is superior to placebo in change from Visit 2 (Week 0) for the following (measured at 88 weeks) for:
 
 Body weight Waist circumference Glycemic control 	
 Mean change in BMI (kg/m²) Mean change in: 
 Fasting glucose (mg/dL) HbA1c (%) Mean change in fasting insulin (pmol/L) Mean change in: 
 Total cholesterol (mg/dL) LDL-cholesterol (mg/dL) Non-HDL-cholesterol (mg/dL) HDL-cholesterol (mg/dL) VLDL-cholesterol (mg/dL) Triglycerides (mg/dL) Free Fatty acids (mg/dL) Mean change in: 
 systolic blood pressure (mmHg) diastolic blood pressure (mmHg) Mean change in SF-36 v2 acute form in: 
 Physical Functioning domain (PF) Role-Physical domain (RP) Role-Emotional domain (RE) Mental Health domain(MH) Mean change in IWQOL-Lite-CT Physical Function composite score 
 Mean change in body weight (kg) Mean percent change in body weight (%) Mean change in BMI (kg/m²) Mean change in waist circumference (cm) Mean change in: 
 Fasting glucose (mg/dL)

Objectives	Endpoints

 • Insulin • Lipid parameters • Blood pressure • Patient-Reported Outcomes 	
 ○ HbA1c (%) • Mean change in fasting insulin (pmol/L) • Mean change in: 
 ○ Total cholesterol (mg/dL) ○ LDL-cholesterol (mg/dL) ○ Non-HDL-Cholesterol (mg/dL) ○ HDL-cholesterol (mg/dL) ○ VLDL-cholesterol (mg/dL) ○ Triglycerides (mg/dL) ○ Free fatty acids (mg/dL) • Mean change in: 
 ○ systolic blood pressure (mmHg) ○ diastolic blood pressure (mmHg) • Mean change in SF-36 v2 acute form in Physical Functioning domain (PF). • Mean change in IWQOL-Lite-CT Physical Function composite score

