Unless specified otherwise, for analyses in the double-blind treatment period, baseline is defined as the last nonmissing data collected prior to or at randomization (Week 36); for analyses including data collected in open-label lead-in period, baseline is defined as the last nonmissing data collected prior to or at study enrollment (Week 0).

For some specific safety related parameters, the definition of baseline and postbaseline for double-blind treatment period are specified in [Table GPHN.4.1](#).

The definition of baseline and postbaseline during the open-label lead-in treatment period can be found in [Appendix 4](#).

Table GPHN.4.1. Baseline and Postbaseline Definitions for Safety Outcomes in Double-Blind treatment Period

Analysis Set	Analysis Type	Baseline	Postbaseline
SS	1.1) Treatment-Emergent Adverse Events	Ongoing at the time of the randomization to the double-blind treatment period.	Starts after randomization visit and ends after the whole study period (including off-drug follow-up visit).
SS	1.2) Treatment-Emergent Abnormal Labs ^a , Vital Signs, and ECGs.	Refer to Table GPHN.6.1 for baseline definition.	Postbaseline will be defined as above (1.1). All scheduled and unscheduled measurements will be included.
SS	1.4) Change from Last Baseline to Week xx and to Last Postbaseline for Labs ^a , Vital Signs, and ECGs.	The last scheduled and unscheduled non-missing assessment recorded during the open-label lead-in period.	Postbaseline will be defined as above (1.1). Only scheduled visits will be included. The ED visits are considered scheduled visits.

Abbreviations: ECGs = electrocardiogram; ED = early discontinuation; SS = Safety Analysis Set.

^a Immunogenicity-related analysis is specified in Section [4.6.5.5](#).

For the primary and key secondary efficacy endpoint analyses subject to type 1 error rate control, data for participants with missing values at the 88-week visit (or weight-related measurements at 64-week visit) will be imputed based on the method described in Section [4.3.2.3](#). Otherwise, missing values will not be explicitly imputed except for the parameters with only 1 postbaseline measure during the analysis period per schedule of activity, where LOCF approach will be applied to impute the endpoint when ED measure is available.

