4.4.3.1. Additional Secondary Efficacy Analyses

Table GPHN.4.3. Secondary Efficacy Measures Not Controlled for Type 1 Error

Analysis variable	Analysis set	Analysis method	Additional Information
Mean change in measurements of lab tests and vital sign	Data from randomization (Week 36) to Week 88	MMRM model with treatment group, visit, treatment-by-visit interaction, all stratification factors as fixed effects, and the corresponding value at randomization (Week 36) as a covariate	Variance-covariance

Analysis variable	Analysis set	Analysis method	Additional Information
			structure for within-patient errors will be same as Section 4.3.2.2. LSM estimates may be plotted by treatment through 88 weeks. Log transformation will be adopted for fasting insulin and lipid parameters.
Mean change in SF-36 v2 acute form domain score in 
 • Physical Functioning domain (PF) • Role-Physical domain (RP) • Role-Emotional domain (RE) • Mental Health domain (MH) Mean change in IWQOL-Lite-CT Physical Function composite score		ANCOVA model with terms of treatment group, all stratification factors, and the corresponding value at randomization (Week 36) as a covariate.	Missing data will be imputed using LOCF.
Mean change in measurements of lab tests and vital signs	Data from Week 0 to Week 88	MMRM model with treatment group, visit, treatment-by-visit interaction, all stratification factors, and the corresponding value at baseline (Week 0) as covariates.	Variance-covariance structure for within-patient errors will be same as Section 4.3.2.2. LSM estimates may be plotted by treatment through 88 weeks. Log transformation will be adopted for fasting insulin and lipid parameters.
Mean change in body weight, BMI, and percent change in body weight		MMRM model with treatment group, visit, treatment-by-visit interaction, country/pooled country and sex as fixed effects, and the corresponding value at baseline (Week 0) and at randomization (Week 36) as covariates.	Variance-covariance structure for within-patient errors will be same as Section 4.3.2.2. LSM estimates may be plotted by treatment through 88 weeks.

Analysis variable	Analysis set	Analysis method	Additional Information

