The mean change from baseline differences among treatments at all scheduled visits will be assessed via an MMRM using REML. Unless specified otherwise, if the safety parameter is assessed at 88 weeks, then the model will include country/pooled country, sex, tirzepatide MTD dose at randomization, percent weight loss at randomization (<10% and $\geq 10\%$), treatment group, visit and treatment-by-visit interaction as fixed effects, and baseline value of the safety parameter as a covariate. To model the covariance structure within participants, the unstructured covariance matrix will be used. If this model fails to converge, the covariance structures specified in

Section 4.3.2.2 will be tested in order until convergence is met. If the data does not warrant the MMRM model, then ANCOVA model will be conducted.

For selected parameters, time-to-first-event analysis via the Cox-proportional hazards model may be conducted. Participants without the event will be censored at the end of study participation.

For participants experiencing the event, the “time-to-first-event” will be the time (in weeks) from first dose or randomization (depends on the event of interest and analysis feature, eg, for time to study discontinuation, time from first dose might be used; for time to AE during double-blind treatment period, time from randomization might be used) to first occurrence of the event.

Where necessary, the rate of events will be analyzed using a generalized linear mixed-effects model assuming the number of events follows a negative binomial distribution and with treatment as a fixed effect. The logarithm of days during the double-blind treatment period will be adjusted as an offset to account for possible unequal treatment duration of follow-up between participants.

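### Lipids and free fatty acids have one scheduled on-treatment draw after randomization, so the by-visit MMRM in SAP Table GPHN.4.3 reduces to an observed-case ANCOVA, and the row does not say whether the SAP 4.1 LOCF rule applies

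*SAP*

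**What the plan says.** **Model.** The Week 36 to Week 88 laboratory row of SAP Table GPHN.4.3 (section 4.4.3.1) specifies an "MMRM model with treatment group, visit, treatment-by-visit interaction, all stratification factors as fixed effects, and the corresponding value at randomization (Week 36") as covariate, with the covariance rule of SAP 4.3.2.2. Lipids belong to this row, because its notes say "Log transformation will be adopted for fasting insulin and lipid parameters". Table GPHN.1.1 lists free fatty acids, "Free Fatty acids (mg/dL"), among the lipid parameters. The row gives no missing-data rule.

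**Schedule.** In Protocol 1.3, the lipid panel and "Free fatty acids" are marked at Visits 1, 2, 8 (Week 24), 11 (Week 36), 24 (Week 88), ED and 801. HbA1c, chemistry and insulin are also drawn at Weeks 52, 64 and 76. Visit 99 has no laboratory tests; its procedures begin with "measurement of weight and waist circumference" and otherwise cover medications, adverse events and mental health questionnaires.

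**Missing data.** SAP 4.1 leaves values unimputed outside the primary and key secondary analyses, "except for the parameters with only 1 postbaseline measure during the analysis period per schedule of activity, where LOCF approach will be applied" when an ED value exists. The patient-reported outcome rows of Table GPHN.4.3 specify ANCOVA and add "Missing data will be imputed using LOCF".

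**Estimand.** SAP 4.4.3 puts these endpoints under the efficacy estimand, which SAP 1.2.1 defines by a hypothetical strategy. The Efficacy Analysis Set (EAS) stops at last dose plus 7 days (SAP section 3).

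**The concern.** An MMRM helps with dropout because earlier on-treatment values of the same variable inform the missing final one. Lipids and free fatty acids have no scheduled value between Week 36 and Week 88, so this benefit is absent and the specified model is not the one that would be fitted.

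Two analyses can then be drawn from the SAP: observed Week 88 cases only (the row read literally), or ANCOVA with the ED value carried forward (section 4.1 read into the row). They use different participants and can give different estimates, and the choice could be made after unblinding. The second also freezes lipids partway through weight regain, whereas the estimand asks what Week 88 would look like had treatment continued. Seven endpoints are affected: total, LDL, non-HDL, HDL and VLDL cholesterol, triglycerides and free fatty acids.

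**Working it through.** **1. The plan's own figure.** SAP section 5 gives a 6% difference, SD 8%, 25% dropout, 300 per arm and two-sided alpha 0.05. Evaluable per arm: 300 × 0.75 = 225. SE = 8 × √(2/225) = 0.754, and 6/0.754 = 7.95, so power exceeds 0.999 and the stated power of more than 90% holds. It concerns the primary endpoint; the documents give no figure for lipids.

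**2. Scheduled post-randomization draws**

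| Parameter | After Week 36, on treatment | Other |
|---|---|---|
| HbA1c, glucose, insulin | Weeks 52, 64, 76, 88 | ED, 801 |
| Lipid panel, free fatty acids | Week 88 | ED, 801 |

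Visit 801 is a safety follow-up visit off drug and lies outside the EAS. An ED value is in the EAS only if taken within 7 days of the last dose.

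**3. The model with one visit.** A design with intercept, treatment, baseline, visit and treatment-by-visit has 5 columns but rank 3, and the covariance matrix is a single variance. In one simulated data set the single-visit MMRM and the observed-case ANCOVA gave the same effect (-0.0787, n = 440). ANCOVA with ED values carried forward gave -0.0704 (n = 600).

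**4. Participants used.** Take the planned dropout rate as the share without an on-drug Week 88 value, and let a be the share of those with a usable ED value. The literal model uses 600 × (1 - dropout). LOCF adds 600 × dropout × a. The documents do not give a.

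| Dropout | Literal | LOCF, a = 0.5 | a = 0.8 | a = 1 | Largest gap |
|---|---|---|---|---|---|
| 15% (assumed) | 510 | 555 | 582 | 600 | 90 |
| 25% (planned) | 450 | 525 | 570 | 600 | 150 |
| 35% (assumed) | 390 | 495 | 558 | 600 | 210 |

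At 25% dropout the literal model's SE is √(600/450) = 1.155 times that of the full 600.

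**5. Size of bias.** No document gives a lipid-weight slope or a dropout mechanism, so both are assumed. With 300 per arm, 0.02 log units per 1% weight, and dropout rising with regain to about 31% on placebo and 23% on tirzepatide, 400 simulated trials gave:

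| Weight difference | True contrast | Observed cases | ED-LOCF |
|---|---|---|---|
| 6% (planned) | -0.120 | -0.112 | -0.107 |
| 12% | -0.241 | -0.224 | -0.210 |

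Imputation from the weight course gave -0.120 in the 6% case. Further runs, with slopes of 0.005 to 0.02 and dropout of about 20-33%, put ED-LOCF at 10-14% too small, observed cases at 2-6% and imputation within about 2%.

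**6. Bias against standard error at the planned 6%.** Weight alone contributes 0.02 × 8 = 0.16 log units of SD.
- With no other lipid noise, SE = 0.16 × √(2/225) = 0.015 for observed cases, against a bias of 0.120 - 0.112 = 0.008.
- For ED-LOCF using all 600, SE = 0.16 × √(2/300) = 0.013, against a bias of 0.120 - 0.107 = 0.013.
- The 14% extreme is 0.14 × 0.120 = 0.017. That is 1.3 SE with zero noise, and below one SE once noise SD exceeds about √((0.0168/0.0816)² - 0.16²) = 0.13.
- With an assumed noise SD of 0.25, total SD = √(0.16² + 0.25²) = 0.297 and SE = 0.297 × √(2/300) = 0.024. ED-LOCF bias is then about 0.5 to 0.7 SE.

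**The case against.** The strongest reply is that the two rules complement each other. The row names a model and is silent on missing data, while SAP 4.1 supplies a rule for exactly this case and allows ANCOVA or MMRM for continuous measures in general. Read together, the plan is ANCOVA with ED-LOCF, as in the patient-reported outcome rows. That is a fair reading, so a reader who infers a flat contradiction goes too far. It is not the only reading. The table specifically chooses MMRM here, and states LOCF for the patient-reported outcomes but not for the laboratory row. The explicit fallback, "If the data does not warrant the MMRM model, then ANCOVA model will be conducted", stands only in the safety sections (SAP 4.6, with a similar sentence in 4.6.3.6). The complementary reading also leads to the rule that fits the estimand worse.

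These counterpoints stand:
- The aliased terms do no numerical harm; the treatment contrast is simply the ANCOVA one.
- Observed-case ANCOVA is unbiased if missingness depends only on the model covariates. A reader might infer that it must miss the efficacy estimand, but that requires a further assumption about dropout.
- The figure of 150 participants is a ceiling. Protocol 7.2 asks for an ED visit on leaving the study only where possible, and the EAS window excludes late samples.
- The simulations generate lipids from weight, so imputation from weight succeeds partly by construction.
- The Week 0 row has lipids at Weeks 24, 36 and 88, so its MMRM has no estimability fault. It is a separate endpoint with a different baseline covariate, and the two rows need not share participants.

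**Conclusion.** The concern holds for the Week 36 to Week 88 laboratory row, for lipids and free fatty acids only. The schedule and the model do not match, the governing missing-data rule is not stated, and the LOCF rule that could fill the gap does not target a hypothetical-strategy estimand. These conclusions need no simulation.

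The size is modest. At 25% dropout the readings differ by 0 to 150 of 600 participants, depending on how many have an in-window ED value. Under the assumed slopes and regain-dependent dropout, ED-LOCF understates the contrast by roughly 10-14% and observed-case analysis by about 2-6%. At the planned 6% weight difference both are about one standard error or less with moderate lipid noise. At an unplanned 12% difference, ED-LOCF bias can exceed one standard error.

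A reader might infer a threat to the trial's main conclusions. The documents do not support that: these are additional secondary endpoints outside type 1 error control, and the primary and key secondary analyses and the sample size are unaffected. The change is still worth making, because a better-aligned analysis is available from data already collected.

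**What to change.** Give lipids and free fatty acids their own row in Table GPHN.4.3 for change from randomization:

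- ANCOVA at Week 88 on the log scale, with treatment, all stratification factors and the Week 36 value, and without by-visit terms or a by-visit plot.
- Multiple imputation of missing Week 88 values under MAR within arm, from prior lipid values, any ED lipid value within last dose plus 7 days, and on-drug post-randomization weights, pooled by Rubin's rules.
- A statement that this replaces the SAP 4.1 LOCF rule for these parameters. LOCF may stay as a sensitivity analysis.

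Leave the Week 0 MMRM row as it is. The cost is a few lines of SAP text and a small amount of extra programming; no new data are needed. If the sponsor prefers not to impute, the minimum is to name ANCOVA for these parameters and state whether the SAP 4.1 rule applies and how ED values relate to the EAS cut-off. That removes the ambiguity, but keeping LOCF would leave the estimand mismatch.

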1. Clarified that the population-level summary for the “difference in response percentage between treatment conditions” is assessed by odds ratio per the US FDA feedback (see [Table GPHN.1.2](#)).
2. Clarified that placebo multiple imputation will be used for missing data imputation in Category 1 for treatment-regimen estimand if there are not enough retrieved dropouts to impute missing data in Category 2 (see [Section 4.3.2.3](#)).
3. Added sensitivity analyses to evaluate the robustness of the primary results with respect to different missing data imputation methods per the US FDA feedback (see [Section 4.3.2.4](#)).
4. Clarified the covariate in the analysis model (see [Section 4.4](#)):
 - For the analyses of endpoints that were compared to the time of “randomization (Week 36)”
 - Weight-related endpoints (ie, weight, BMI): stratification factors (except percentage weight loss at randomization [Week 36]) and corresponding value at randomization (Week 36) were included as covariates.
 - Other endpoints: all stratification factors and corresponding values at randomization (Week 36) were included as covariates.
 - For the analyses of endpoints that were compared to the time of “baseline (Week 0)”
 - Weight related endpoints (ie, weight, BMI): stratification factors (except percentage weight loss at randomization [Week 36]) and corresponding values at randomization (Week 36) and at baseline (Week 0) were included as covariates.
 - Other endpoints: all stratification factors and corresponding values at baseline (Week 0) were included as covariates.

1. Introduction

The main SAP focuses on describing the analysis plan for the double-blinded treatment period. Details of the analysis plan for the open-label lead-in period can be found in [Appendix 4](#). Changes to the protocol-planned analyses are described in Section [4.9](#).

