4.4.2. Key Secondary Efficacy Analyses Subject to Type 1 Error Rate Control

Table GPHN.4.2. Secondary Measures Controlled for Type 1 Error

Objectives	Relative to the efficacy measure:	Analysis conducted in a manner similar to	Additional Information
Tirzepatide MTD QW is superior to placebo:	Mean change in body weight (kg) from randomization (Week 36) to Week 88	For treatment regimen estimand: ANCOVA model described in Section 4.3.2.1. For efficacy estimand: MMRM model described in Section 4.3.2.2.	LSM estimates will be plotted by treatment through 88 weeks.
	Mean change in waist circumference (cm) from randomization (Week 36) to Week 88	For treatment regimen estimand: ANCOVA model with terms of treatment group, stratification factors, and corresponding value at randomization (Week 36) as covariates. For efficacy estimand: MMRM model with treatment group, visit, treatment-by-visit interaction, all stratification factors as fixed effects, and corresponding value at randomization (Week 36) as covariates.	LSM estimates will be plotted by treatment through 88 weeks. Refer to Sections 4.3.2.1 and 4.3.2.2 for analysis approach detail.
	Percentage of participants who maintain $\geq 80\%$ of the body weight lost during the 36 weeks of open-label period	For both treatment regimen and efficacy estimand: Logistic regression model will be conducted.	Refer to Section 4.4.1 for analysis approach detail.
Tirzepatide MTD QW is superior to placebo:	Percentage of study participants who achieve $\geq 5/10/15/20\%$ body weight reduction from Visit 2 (Week 0) to Week 88	For both treatment regimen and efficacy estimand: Logistic regression model will be used.	Refer to Section 4.4.1 for analysis approach detail.
	Time (in weeks), during the 52-week double-blind treatment period, to first occurrence of participants returning to $>95\%$ baseline weight for those who have already lost $\geq 5\%$ since Week 0	For both treatment regimen and efficacy estimand: Cox-proportional hazards model will be used with the terms of treatment group (tirzepatide MTD and placebo), country/pooled country, sex, tirzepatide MTD dose at randomization, and weight at randomization (Week 36) and at baseline (Week 0) as covariates.	Only for participants with at least 5% body weight loss during the open-label lead-in period. For treatment regimen estimand: the participant without event will be censored at Week 88.

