Mean change in waist circumference		MMRM model with treatment group, visit, treatment-by-visit interaction, all stratification factors as fixed effects, and the corresponding value at baseline (Week 0) as covariates.	Variance-covariance structure for within-patient errors will be same as Section 4.3.2.2. LSM estimates may be plotted by treatment through 88 weeks.
Mean change in SF-36 v2 acute form in 
 Physical Functioning domain (PF) and 
 IWQOL-Lite-CT in 
 Physical Function composite score 		ANCOVA model with terms of treatment group, all stratification factors, and the corresponding value at baseline (Week 0) as covariates.	Missing data will be imputed using LOCF.

Abbreviations: ANCOVA = analysis of covariance; BMI = body mass index; IWQOL-Lite-CT = Impact of Weight on Quality of Life-Lite-Clinical Trials Version; LOCF = last observation carried forward; LSM = least squares mean; MMRM = mixed model for repeated measures; SF-36 v2 acute form = Short Form-36 Version 2 Health Survey acute form.

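### The change-from-Week-0 models for waist, labs, vital signs and PROs omit the endpoint's own value at randomization (Week 36), which costs precision but causes no bias

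*SAP*

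**What the plan says.** SAP Section 4.4.3.1, Table GPHN.4.3, sets out these models for change from Week 0 to Week 88:

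- Waist circumference, MMRM: "all stratification factors as fixed effects, and the corresponding value at baseline (Week 0) as covariates".
- Labs and vital signs, MMRM: "all stratification factors, and the corresponding value at baseline (Week 0) as covariates".
- SF-36 Physical Functioning and IWQOL-Lite-CT Physical Function: "ANCOVA model with terms of treatment group, all stratification factors, and the corresponding value at baseline (Week 0) as covariates".
- Body weight, BMI and percent change in weight, MMRM: "the corresponding value at baseline (Week 0) and at randomization (Week 36) as covariates".

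The split is deliberate. Item 4 of the Version 3 changes in the SAP version history gives the rule for endpoints not related to weight: "Other endpoints: all stratification factors and corresponding values at baseline (Week 0) were included as covariates". No reason is stated.

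The same endpoints are also analysed as change from randomization, with the Week 36 value in the model:

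- Waist, a key secondary endpoint (Table GPHN.4.2): "all stratification factors as fixed effects, and corresponding value at randomization (Week 36) as covariates".
- Labs and vital signs (Table GPHN.4.3): "all stratification factors as fixed effects, and the corresponding value at randomization (Week 36) as a covariate".
- PROs (Table GPHN.4.3): "ANCOVA model with terms of treatment group, all stratification factors, and the corresponding value at randomization (Week 36) as a covariate".

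**The concern.** SAP Section 4.1 takes the last value at or before randomization as the baseline for the double-blind period. The Week 36 value is therefore a pre-randomization covariate, and adjusting for it is valid. Without it, whatever part of the Week 88 outcome is predicted by Week 36 but not by Week 0 stays in the error term. A chance difference between the arms at Week 36 also passes into the estimate.

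Two things are at stake. Confidence intervals for supportive results may be wider than they need be. The report will also show two rows for each of these endpoints that estimate the same between-arm difference and do not agree, with nothing in the plan to say why.

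**Working it through.** **1. The plan's own figure.** The documents give no SD, correlation or precision figure for these endpoints. The only power statement is for the primary endpoint (Protocol Section 9.2, SAP Section 5): difference 6, SD 8, 300 per arm, 25% dropout, power above 90%. With 225 per arm, SE = 8 × √(2/225) = 0.754 and 6/0.754 = 7.95, so power exceeds 0.999. The statement is reproduced, and this point does not touch it.

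**2. Both rows estimate the same contrast.** Write Y0, Y36 and Y88 for the values at the three weeks. Subtracting a covariate that is already in a linear model leaves the treatment coefficient unchanged:

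- Y88 − Y0 adjusted for Y0 gives the same treatment coefficient as Y88 adjusted for Y0.
- Y88 − Y36 adjusted for Y36 gives the same treatment coefficient as Y88 adjusted for Y36.

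Both target the between-arm difference at Week 88, on the log scale where the SAP logs the variable. They differ only in which pre-randomization value they adjust for.

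**3. Gain from adding Week 36.** Let a, b and c be the correlations of Week 0 with 36, Week 36 with 88, and Week 0 with 88. The partial correlation of Week 36 with Week 88 given Week 0 is

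r = (b − ac) / √[(1 − a²)(1 − c²)],

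and SE with Week 36 / SE without = √(1 − r²). For a = b = c = 0.7, r = (0.7 − 0.49)/0.51 = 0.412, r² = 0.170 and √0.830 = 0.911, so the SE falls 9%.

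The correlations below are assumptions.

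| a (0–36) | b (36–88) | c (0–88) | r | Variance lower by | SE lower by |
|---|---|---|---|---|---|
| 0.3 | 0.3 | 0.3 | 0.23 | 5% | 3% |
| 0.9 | 0.8 | 0.8 | 0.31 | 9% | 5% |
| 0.5 | 0.5 | 0.5 | 0.33 | 11% | 6% |
| 0.7 | 0.7 | 0.7 | 0.41 | 17% | 9% |
| 0.8 | 0.8 | 0.7 | 0.56 | 31% | 17% |
| 0.9 | 0.9 | 0.8 | 0.69 | 47% | 27% |
| 0.7 | 0.8 | 0.55 | 0.70 | 48% | 28% |

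A more extreme set, (0.5, 0.92, 0.4), would give 58%, so the table is a range of plausible cases and not a bound.

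**4. Allowing for the strata.** The models already contain the Week 36 dose and the weight-loss category (<10% or ≥10%). A simulation with 225 per arm and 2000 replicates put the weight-loss stratum in the model first. The Week 36 value still lowered the variance by 8–13% (all correlations 0.5), 12–18% (all 0.7), 23–30% (0.8/0.8/0.7) and 40–51% (0.9/0.9/0.8). The true effect was zero, and the mean estimates were close to zero with and without Week 36, so there is no bias.

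**5. How far the two planned rows can differ.** With unit variances and the strata ignored, the difference between the Week 0-adjusted and Week 36-adjusted estimates is the between-arm difference in bY36 − cY0. Its variance is proportional to b² + c² − 2abc. With all correlations 0.7 this is 0.98 − 0.686 = 0.294, against a residual variance of 1 − 0.49 = 0.51 in the Week 0 row. The SD of the difference is √(0.294/0.51) = 0.76 of the Week 0 row's SE. A visible disagreement between the rows would be ordinary chance.

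**The case against.** The strongest reply has four parts.

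- **The rule is prespecified and has a structure.** Weight-related models drop the weight-loss stratum and carry the Week 0 and Week 36 values instead, while other endpoints keep the stratum. This stands as description, so the weight/BMI row is not a perfect precedent. But a two-level weight-loss category does not replace the Week 36 blood pressure, HbA1c, waist or SF-36 score.
- **A Week 36-adjusted contrast is already planned for each endpoint.** This stands and limits the consequence. That row is the more precise of the two only when Week 36 predicts Week 88 better than Week 0 does, and it does not make the Week 0-based row efficient.
- **Week 36 may predict less well in the placebo arm.** If values drift back toward Week 0 after withdrawal, the gain shrinks. This is possible, and it is one reason to give a range.
- **These are supportive analyses.** The table is headed as outside type 1 error control, and SAP Section 2.1 makes no multiplicity adjustment for them. This stands.

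A reader might infer a uniformly large gain, such as 13–31% off the SE for all these endpoints. The documents do not support that, because they give no correlations and reasonable values yield about 5% as readily as 30%. A reader might also infer that imbalance at randomization is left wholly uncorrected, or that the estimates are biased. Neither follows: the strata correct part of the imbalance, and randomization keeps the contrast unbiased.

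**Conclusion.** The point holds as one of efficiency and consistency. Three rows of Table GPHN.4.3 omit a valid covariate that the plan already uses for the same endpoints elsewhere, and no reason is given. The cost is potentially material, roughly 3% to 30% of the SE, about 9% with all correlations at 0.7. It is small where the partial correlation given Week 0 is 0.3 or less (under 10% of variance) and substantial where it is 0.5 or more (25% of variance or more). It will differ between waist, labs, blood pressure and PROs. These figures rest on assumed correlations, a common covariate slope in both arms and complete data. No primary or key secondary conclusion depends on the change.

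**What to change.** - In the three Week 0-to-Week 88 rows (labs and vital signs, waist, PROs), add the endpoint's value at randomization (Week 36) as a covariate beside the Week 0 value, on the log scale where the response is logged.
- State that the MMRM responses are post-randomization visits only. The table gives the analysis set as data from Week 0 through Week 88, and Week 36 cannot be both a response and a covariate. The weight/BMI row needs the same statement.
- Align the rule for other endpoints in the version history, or state why these endpoints are treated differently from weight and BMI.

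The two rows will still differ somewhat after this, because the change-from-randomization models carry Week 36 alone. By the identity in step 2 they would coincide if both rows used both values and the same records and visits. A footnote saying that both rows estimate the same Week 88 difference would be enough.

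The cost is one covariate per model, about one degree of freedom. The companion models already require the Week 36 values, so no new data are needed.
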